2.7 Quality control and quality assurance

The operators of the centers for specific acupuncture treatment must have the qualifications of the acupuncturist and are independent of the clinical treatment for more than 2 years. In order to ensure the smooth progress of the research, the first month before the clinical trial is officially launched, the research team will convene and complete the special clinical training, and conduct unified training for the clinical researchers of the two centers. Key train is carried out on that implementation of the subject and the Standard Operation Procedure (SOP) and gauge evaluation so that each clinical researcher is familiar with the research process and detailed implementation rules to improve the internal observation consistency of the researcher and the consistency between the observers, to ensure the reliability of the clinical study conclusion.

All observations and findings in clinical studies should be verified and confirmed repeatedly to ensure the reliability and authenticity of the data and to ensure that the

results and conclusions of clinical research are derived from the original data.

The appointment of specialized personnel for experimental data collection and statistics will control the test bias.

The quality control measures of each center. Regular monitoring of the two centers will be used to control the center-to-center bias.

2.8 Measures to improve the compliance of subjects

The compliance of patients was measured by the number of treatments. The calculation formula is as follows:

Criteria are the number of treatments that the subject has received over 80 percent of the treatment (including 80%).

In order to obtain a better compliance and make the final summation of the patient is not less than 80% of the total number of cases in the trial, so the following measures are adopted to improve patient compliance: Adhere to the principle of voluntary, sign the patient informed consent; We will improve and maintain the patient's compliance with the medical quality, the medical treatment environment, the medical expenses, etc., and encourage patients to persist in treatment during the study period; Provide the patient with a certain amount of transportation expenses and labor costs; Pay attention to the establishment of a good doctor-patient relationship, explain the purpose and necessity of the examination, treatment and review to the included cases, and obtain the consent and cooperation of the patients . Record the patient's contact information in detail for follow-up.

[figure not shown]
Part3. The key technology

1. The establishment of an effective treatment program of EA therapy for CTN is the first key technology in the study. The therapy technologies including acupoints selection, needling technique, EA parameters selection, needle retaining time, treatment frequency and how to apply acupuncture combined with carbamazepine.

2. The study design and the quality control of the clinical study is another key technique in this project. Grasping the above key technologies will help to develop a scientific and standardized research program at home and abroad, which can provide a

higher level of evidence-based medical evidence for the clinical effect of CTN by EA therapy.

Technical Route:

Statistical Analysis Plan

1. Data entry and storage

1.1 Data entry

(1) The original data collection:

All observation scales will be measured on a "one to one" basis according to the unified standard, and the subject will be completed independently under the guidance of the doctor to ensure complete and correct completion. In the spot, check whether the filling quantity is perfect and accurate. If any omission/review or blurring is found, check the gauge in time and verify the quality of the recovery gauge strictly.

(2) Data entry and statistics:

The Excel spreadsheet is used to record the data and ensure the original data is accurate and reliable. The special personnel shall carry out the statistics and the research managers shall verify the statistical methods, analysis and discussion without error.

1.2 Data storage

(1) The special person is responsible for the management of various documents, and there are special folders for storage in dedicated files, so that the test researcher can view it, and have access and access records.

(2) The test documents shall be protected strictly in accordance with the confidential management principles.

(3) Test file is available for test researchers and relevant researchers view, and other irrelevant personnel shall not be entitled to refer to.

(4) The equipment of storing test files has safety measures such as insect repellent, fire prevention, moisture-proof and anti-theft.

2. Statistical processing

2.1 Analysis data set

(1) Full Analysis Set (FAS):

A collection of all randomly assigned and at least one treated case. When analyzing the main therapeutic indicators, the missing values in the FAS set were

transferred to the current (LOCF) method by using the results observed at the latest time point. The Available Case Analysis principle was used in the Analysis of secondary efficacy indicators, general conditions and safety Analysis.

(2) Per Protocol Set (PPS):

Compliance set refers to meet the inclusion criteria and follow the test protocol to complete the treatment of the set of cases, which is consistent with the test protocol, compliance, did not take prohibited drugs, to complete the evaluation of effectiveness (at least the main outcome) cases.

(3) Security Analysis System (SAS):

At least one treatment is received and the actual data of the safety indicator evaluation record is available.

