1.5 Removed criteria

The subjects who have entered a group of research but who were met one of the following conditions should be removed:

- 1) Those who do not meet exactly with the inclusion and exclusion criteria of the trial.
- 2) There are obviously adverse reactions during the treatment.

3) The subjects are not treated according to the treatment plan of the group after they have entered.

The removed cases should indicate the reason and retained the original medical records. No participation of statistical analysis of efficacy, but those who have received at least one treatment can participate in analysis of adverse reaction.

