1.6 Shedding criteria

Cases that have been entered but not completed the treatment program should be considered as falling off, Such as the following situations:

- 1) Patient withdraws or has been lost their visit.
- 2) The acupuncture treatment has not reached 80%.
- 3) In the treatment, there are serious adverse reactions or adverse events.

The shedding cases should explain the reasons. If the case has been recorded the baseline data, and received at least one time acupuncture treatment, the results of its final main outcome can be carried out for statistical analysis. The medical records should be retained, while the data should not be carried forward during the follow-up.

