2.2 Statistical analysis content

The main analysis contents include:

(1) Four groups of cases distribution: Four groups of the total loss rate and the loss due to adverse events off rate comparison.

(2) Comparability analysis: Compare demographic data and other baseline values to measure the comparability of the four groups.

(3) Compliance analysis: The four groups of patients were compared according to the amount of time to receive the appropriate treatment, the program did not use prohibited drugs.

(4) Effectiveness analysis: Main therapeutic indexes are analyzed by PP and ITT simultaneously. Since this study is a multi-center clinical trial, the effect of the central effect and baseline on the therapeutic effect should be taken into account in the analysis.

(5) Effect factor analysis: such as age, gender, duration, combined medication and other factors on the efficacy.

(6) Safety analysis: First, according to the requirements of adverse reaction correlation list describes four groups of adverse events and adverse reactions (including the number of cases of adverse events and laboratory examination indexes before and after the test "normal turn abnormal cases and different rate), statistical

analysis of the adverse reactions by chi-square test.

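### The SAP and protocol disagree on which treated patients enter the 6-month full analysis, and on whether missing values are carried forward

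*Combined protocol and SAP*

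**What the plan says.** **Who is analysed.** SAP 2.1 defines the FAS as "A collection of all randomly assigned and at least one treated case". SAP 2.2(4) adds "Main therapeutic indexes are analyzed by PP and ITT simultaneously", but neither document says that ITT means the FAS.

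Protocol 1.5 lists three grounds for removal after entry: failing the eligibility criteria, "There are obviously adverse reactions during the treatment", and not being treated to the group's plan. For removed cases it prescribes "No participation of statistical analysis of efficacy". Those treated at least once stay in the adverse-reaction analysis only.

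Protocol 1.6 covers shedding: withdrawal or loss, less than 80% of the acupuncture, or cases where "there are serious adverse reactions or adverse events". If such a patient has baseline data and one or more acupuncture sessions, "the results of its final main outcome can be carried out for statistical analysis".

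**With what value.** In the FAS, missing main-outcome values are "transferred to the current (LOCF) method by using the results observed at the latest time point". For shed cases, protocol 1.6 says "the data should not be carried forward during the follow-up".

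**The outcome affected.** The first main outcome in protocol 2.6 is change in VAS at 6 months. Treatment lasts 4 weeks. After that, diaries are kept only in weeks 11–12 and 23–24.

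**The concern.** Two of the three removal grounds arise after randomisation, and both can be consequences of treatment. If 1.5 is followed as written, the full-analysis result loses those patients and with them the protection of randomisation. Removal may differ by group: protocol 2.6(4) lists reactions specific to carbamazepine, which two of the four groups take as assigned treatment.

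The second difficulty is the value used at month 6. Objective 2 asks about the long-term and post-treatment effect. Carrying an earlier score to month 6 assumes that pain did not change in between, which is what the objective sets out to learn. If 1.6 instead forbids this for shed patients, no rule says what value they receive.

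Two statisticians working from these documents could build different month-6 ITT datasets, and each could cite the text in support.

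**Working it through.** **1. Membership, rule by rule.** All patients below are randomised and treated at least once.

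| Patient | Protocol 1.5 | Protocol 1.6 | SAP 2.1 FAS |
|---|---|---|---|
| Obvious but not serious adverse reaction | out | silent, unless treatment was not completed | in |
| Obvious and serious adverse reaction | out | may be analysed | in |
| Under 80% of acupuncture | out, if this counts as not treated to plan | may be analysed | in |
| Found ineligible after entry | out | silent | in |

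The 1.6 column assumes baseline data and one or more acupuncture sessions. Every row has a conflict or a possible one, and no section says which rule prevails.

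**2. Value at weeks 23–24 when that diary is missing.**
- If SAP 2.1 governs, a patient with no follow-up diary receives a value from week 4 or earlier. A patient last seen at 3 months receives the weeks 11–12 value.
- If 1.6 bars carry-forward, shed patients have no stated rule.
- If 1.6 means only that shed patients are not followed further, it does not contradict LOCF, but their later pain is then never observed.

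LOCF alters only missing values. A removed or shed patient with a weeks 23–24 diary is unaffected by it.

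**3. Scale of removal (illustration).** The plan gives no figure on this point, so the shares and differences are assumptions. Change in a side's mean = share removed × difference between removed and kept patients. For one side of 60 (two groups of 30) and a difference of 1 to 2 points:
- 5% (3 patients): 0.05 to 0.10 points
- 10% (6 patients): 0.1 to 0.2 points
- 20% (12 patients): 0.2 to 0.4 points

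**4. Scale of LOCF (illustration).** Inputs from protocol 2.1: SD 1.6, and a 20% allowance, which reproduces as 24/(1 − 0.20) = 30 per group. That allowance covers shedding and other factors; it is not a forecast for month 6. Assumptions: no true difference at month 6; one side better by d = 0, 1 or 2 points at week 4, fully faded by month 6; a share m missing at random and equally on both sides.

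Bias = m × d. If half of those missing were last seen at 3 months, when half the fade has occurred, bias = m × (0.5d + 0.25d) = 0.75md.

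Two-sided error at 0.05, from 100,000 simulated trials per case, for d = 0 / 1 / 2:

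| Missing | Bias (points) | 60 v 60 | 30 v 30 |
|---|---|---|---|
| 20%, all last seen at week 4 | 0 / 0.2 / 0.4 | 4.9 / 10.1 / 24.5% | 5.0 / 7.6 / 14.4% |
| 10%, all last seen at week 4 | 0 / 0.1 / 0.2 | 4.9 / 6.4 / 10.0% | 5.0 / 5.6 / 7.4% |
| 20%, half last seen at 3 months | 0 / 0.15 / 0.30 | 5.0 / 8.1 / 16.5% | 5.0 / 6.3 / 10.4% |

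Hand check of the largest entry: the variance on the carried side is 1.6² + 0.2 × 0.8 × 2² = 2.56 + 0.64 = 3.20. The standard error is √((3.20 + 2.56)/60) = 0.31, and 0.4/0.31 = 1.29. The rejection rate is about Φ(1.29 − 1.96), or 25%, in line with 24.5%. Analysing only observed month-6 values in the same trials gave no bias and 4.8 to 5.1% error.

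Without fade there is no excess error. With other dropout patterns the bias can run the other way: a responder who relapses keeps a low score, while a patient who leaves in unrelieved pain keeps a high one.

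**The case against.** The strongest defence is that 1.5 was probably meant for the per-protocol set. The PPS definition in SAP 2.1 largely mirrors the removal list, and planning PP and ITT together shows that an inclusive analysis was intended. Statisticians are blinded (protocol 2.3) and both results are to be reported, which limits data-driven choice. LOCF is prespecified. Differential removal is possible but not shown: needling reactions can occur in all four groups because the sham is also needled, and removal for ineligibility need not depend on treatment.

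Much of this stands, and it makes the membership repair one of wording. It does not remove the conflict. The bar in 1.5 is not limited to the PPS, and blinding does not say which patients and values make up the ITT result. The PPS cannot stand in for it, since it omits the patients in dispute.

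A reader might infer that the plan will certainly enter treatment-period pain as the 6-month outcome. The documents do not support that. Protocol 1.6 may forbid it for shed patients, and anyone last seen at 3 months would carry a follow-up value.

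**Conclusion.** The concern holds as two document conflicts affecting the 6-month full-analysis result.

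- **Membership (high confidence).** SAP 2.1 includes patients whom protocol 1.5 excludes from all efficacy analysis, and 1.6 overlaps with 1.5. This must be settled before analysis.
- **Carry-forward (moderate confidence, because 1.6 is unclear).** Either SAP 2.1 and 1.6 contradict each other, or 1.6 ends follow-up and leaves LOCF in place. The wording must be reconciled.

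Using LOCF as the primary method is a separate weakness that should be fixed, but its urgency is lower.

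The size and direction of any bias are unknown. The documents give no dropout by group and no course of pain after week 4. A reader might take the 24.5% as this trial's error rate, or conclude that the plan favours electroacupuncture; neither follows. That figure needs 20% missing, all last seen at week 4, a 2-point effect entirely gone by month 6, and a 60 v 60 contrast that the plan never names. The verdict rests on the conflicting text, not on these figures.

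**What to change.** **Must be fixed**
1. Use one wording in protocol 1.5, 1.6, SAP 2.1 and SAP 2.2(4): *FAS (the ITT analysis): every randomised patient treated at least once, in the randomised group, with all observed diary data; removal or shedding affects only the PPS.* This concerns analysis only and leaves decisions on stopping treatment untouched.
2. Reconcile 1.6 with SAP 2.1 on carry-forward, and state whether removed and shed patients still provide the weeks 11–12 and 23–24 diaries.

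**Should be fixed, separately**

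3. For the 6-month VAS, prespecify one primary method in place of LOCF. It can be a likelihood-based repeated-measures model with baseline VAS and centre, or multiple imputation followed by the analysis of covariance already named in SAP 2.3. Keep LOCF as a sensitivity analysis.
4. Add a delta-adjusted multiple imputation to show how the conclusion responds to departures from missing at random; it does not test that assumption. State in which groups the shifts apply, include shifts that differ by group, and cap values at VAS 10.

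**Cost.** Wording and modest programming. Under random, equal missingness, intervals are wider than with complete data by about √(1/0.9) − 1 = 5% at 10% missing, or √(1/0.8) − 1 = 12% at 20% missing. These are approximations, not upper bounds. If shed patients currently give no later diaries, no model can recover their pain, and collecting those diaries would be an added cost.

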2.2 Statistical analysis content

The main analysis contents include:

(1) Four groups of cases distribution: Four groups of the total loss rate and the loss due to adverse events off rate comparison.

(2) Comparability analysis: Compare demographic data and other baseline values to measure the comparability of the four groups.

(3) Compliance analysis: The four groups of patients were compared according to the amount of time to receive the appropriate treatment, the program did not use prohibited drugs.

(4) Effectiveness analysis: Main therapeutic indexes are analyzed by PP and ITT simultaneously. Since this study is a multi-center clinical trial, the effect of the central effect and baseline on the therapeutic effect should be taken into account in the analysis.

(5) Effect factor analysis: such as age, gender, duration, combined medication and other factors on the efficacy.

(6) Safety analysis: First, according to the requirements of adverse reaction correlation list describes four groups of adverse events and adverse reactions (including the number of cases of adverse events and laboratory examination indexes before and after the test "normal turn abnormal cases and different rate), statistical

analysis of the adverse reactions by chi-square test.

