2.1 Sample size estimation

The glmpower process of SAS9.3 software is applied to estimate the sample size. According to the literature and the preliminary experiment, the mean values of the

VAS score of EA+Carbamazepine group, EA+Placebo group, sham EA+Carbamazepine group, sham EA+Placebo group were 5.23,4.45,5.50,0.00. The standard deviation was 1.6. Under the condition of $\alpha=0.05$, the test efficiency $1-\beta=0.8$, the four groups were allocated with the 1:1:1:1 proportion, the sample size of each group was calculated at least 24. Considering the existence of shedding and other factors, in the premise of guaranteeing the minimum sample size, the sample size was enlarged by 20% to 30 cases in one group, in total 120 cases for 4 groups. Because of the complexity of the sample calculation process of factorial design, the formula is not listed here.

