2.3 Statistical analysis method

(1) The measurement data: First of all, the normality test was used. For normal distribution, the t-test, paired t-test, variance analysis and covariance analysis were used to check the data. For non-normal distributions, using rank sum test and paired rank sum test.

(2) The enumeration data: Using the chi-square test, Fisher exact test and so on. The hierarchical data are analyzed by Redit, CMH or other non-parametric tests.

(3) Multi-centers analysis of comprehensive efficacy: The CMH method was used for counting data; Analysis of covariance is used for metering data.

(4) All the statistical tests were double-sided, and the p-value is less than or equal to 0.05 and the difference is statistically significant.

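### The adverse-reaction test in SAP 2.2(6) makes no use of the 2x2 factorial design; prespecified EA and carbamazepine contrasts would be a cheap improvement

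*Combined protocol and SAP*

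**What the plan says.** Protocol Part 1 makes the safety of EA part of the first objective. Protocol 2.1 calls the design factorial, states that "the four groups were allocated with the 1:1:1:1 proportion" and plans 30 per group. Under Protocol 2.4 every patient receives needling (EA or sham) and tablets (carbamazepine or placebo).

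SAP 2.2(6) plans, "according to the requirements of adverse reaction correlation list describes four groups of adverse events and adverse reactions", and then "analysis of the adverse reactions by chi-square test". It names no contrast, degrees of freedom, main effect or interaction. SAP 2.2(1) likewise compares loss rates, in total and due to adverse events, over four groups.

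SAP 2.3(2) gives the general rule for counts: "The enumeration data: Using the chi-square test, Fisher exact test and so on". Under the multi-centre efficacy heading, SAP 2.3(3) adds that "The CMH method was used for counting data". SAP 2.3(4) sets the level: "All the statistical tests were double-sided, and the p-value is less than or equal to 0.05".

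Protocol 2.6(4) keeps separate lists for needling events and for carbamazepine reactions. Nausea and vomiting appear on both.

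**The concern.** In a 2x2 design the randomised evidence on EA harm is 60 EA v 60 sham patients, and on drug harm 60 carbamazepine v 60 placebo patients. A four-group test uses neither comparison directly. It spreads a one-factor effect over three degrees of freedom, and a significant result does not identify the factor. A real excess from one treatment is then more likely to be reported as no significant difference in adverse reactions, on a question that belongs to the first objective.

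If the SAP is read as leaving the contrast open, a different problem arises. The analyst could choose among a four-group test, six pairwise tests and two factor comparisons after seeing the data.

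**Working it through.** **Inputs.** From the documents: four arms, 1:1:1:1, 30 per arm (Protocol 2.1; the step from 24 to 30 reproduces as 24/(1 - 0.20) = 30), two-sided 0.05 (SAP 2.3(4)). The documents state no power and no event rate for safety, so there is no safety figure to reproduce and all rates below are assumptions.

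**Tests compared.**

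- Four-group Pearson chi-square, 3 df: X² = 30 Σ(p_j - p̄)² / [p̄(1 - p̄)], where p_j are the arm proportions and p̄ is their mean.
- Factor test, 1 df: CMH over the two levels of the other factor. In each stratum of 30 v 30, with a_k events in the active arm and m_k events in total, the statistic is [Σ(a_k - m_k/2)]² / ΣV_k, with V_k = 30·30·m_k(60 - m_k)/(60²·59).

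**Analytic check, 10% v 30%, one causal factor.** p̄ = 0.20 and Σ(p_j - p̄)² = 4 × 0.10² = 0.04. The noncentrality is 30 × 0.04/0.16 = 7.5. That gives about 78% power on 1 df and 62% on 3 df, a gap of 16 points. In general, a noncentrality giving 80% on 1 df gives 64% on 3 df, and one giving 90% gives 78%.

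**Simulation, one causal factor, 200,000 trials per row.**

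| Assumed rates | Four-group, 3 df | Factor test at 0.05 | Gap | Factor test at 0.025 | Gap |
|---|---|---|---|---|---|
| 10% v 25% | 41% | 59% | 18 | 47% | 6 |
| 10% v 30% | 64% | 80% | 16 | 71% | 7 |
| 10% v 35% | 82% | 93% | 11 | 88% | 6 |
| 5% v 20% | 53% | 73% | 20 | 62% | 9 |
| 3% v 15% | 43% | 68% | 25 | 53% | 10 |

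Outside these rates the gap varies widely: about 5 points at 10% v 40%, under 1 at 10% v 50%, 8 to 9 at 5% v 10%, and 42 at 0% v 10%. The largest gaps occur at low background rates, where the chi-square approximation is poor. For 3% v 15% the expected count under the null is 30 × 0.09 = 2.7 per arm.

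**Other patterns** (arms: both active, EA only, carbamazepine only, neither).

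| Arms | Four-group | Each factor test at 0.05 | Either factor test at 0.05 |
|---|---|---|---|
| 30/20/20/10% | 33% | 28% | 48% |
| 40/25/25/10% | 62% | 49% | 75% |
| 30/10/10/10% | 55% | 34% | 52% |
| 40/10/10/10% | 86% | 61% | 80% |

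When both factors add risk, each factor test alone is weaker than the four-group test, but the chance that at least one is significant is higher. When only the combination arm has an excess, the four-group test is stronger on either count.

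**False positives.** With equal rates of 5%, 10% or 20% in all arms, each factor test rejects in about 5% of trials. At least one of the two rejects in 9% to 10%. The four-group test rejects in about 3% to 5%.

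**Precision of the interaction.** For 30/10/10/10% the interaction on the risk-difference scale is 0.30 - 0.10 - 0.10 + 0.10 = 0.20. Its standard error is √[(0.21 + 3 × 0.09)/30] = 0.126, so the 95% interval is about ±25 points. The estimate shows the pattern but is not a sensitive test.

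**The case against.** The strongest reply is that the plan does not commit to the test criticised. In SAP 2.2(6) the phrase about four groups governs the listing. A 60 v 60 chi-square would fit the wording, and SAP 2.3(2) leaves the method open. This stands: a reader might infer that a single 3-df test is prescribed, but that is the natural reading, not a stated fact.

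Three further inferences go too far.

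- *The plan loses 11 to 25 points of power.* This is conditional on assumed rates and one causal factor. Part of the gap comes from running two tests at 0.05 in place of one.
- *The four-group test is the least sensitive available.* It is more sensitive when only the combination arm has an excess. A joint contribution from both factors is not far-fetched for symptoms on both lists.
- *The trial cannot say which treatment caused the harm.* Needling and drug events are recorded on separate lists, the SAP appears to plan a relatedness listing, and both factor comparisons can be read from the four-arm table.

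The last reply has a limit. Relatedness helps least for the overlapping symptoms. Protocol 2.6(4) also has the acupuncture physician record adverse events, and Protocol 2.3 accepts that the treating doctor is hard to blind. That judgement cannot replace a randomised contrast.

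A final caution is that Protocol 2.5 allows emergency carbamazepine without restriction by arm. Carbamazepine v placebo therefore compares assignment, not clean exposure.

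**Conclusion.** The point holds in a limited form. The SAP specifies no safety contrast that uses the factorial structure, and on the natural reading its test does not by itself separate EA from carbamazepine. For a single-factor excess at the assumed rates of 10% v 25-35% or 3-5% v 15-20%, with 30 per arm and no interaction, it has about 11 to 25 points less power than the matching factor test at 0.05, and about 6 to 10 points less if the two factor tests share alpha. The documents cannot confirm those rates, and the ordering reverses for an excess confined to the combination arm. This is a cheap improvement to a secondary analysis for which no power was planned, not an error that undermines the trial.

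**What to change.** In SAP 2.2(6), keep the four-arm table and the four-group comparison, labelled descriptive. Prespecify two contrasts for adverse reactions: carbamazepine v placebo stratified by EA/sham, and EA v sham stratified by carbamazepine/placebo. Use CMH, or exact stratified methods when counts are sparse. SAP 2.3 already names CMH, but not for this purpose, so the stratification must be written out. Report each contrast with a risk difference and a 95% confidence interval, plus an interaction estimate. Apply the same two contrasts to the loss rates in SAP 2.2(1). State whether the two tests are adjusted for multiplicity, and that they compare groups as assigned.

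The cost is SAP wording and a few lines of code. The downsides are a 9% to 10% chance of at least one false positive per reaction if unadjusted, and less power for an excess confined to the combination arm. The retained table and the interaction estimate would show such an excess, though imprecisely.

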ID: 2018ZY008-CTN

Research name:

*Electroacupuncture Therapy for Change of Pain in
Classical Trigeminal Neuralgia*

Date: June 20, 2018

Electroacupuncture Therapy for Change of Pain in Classical Trigeminal Neuralgia

Study Protocol

Part1. Study objectives

1. To observe the therapeutic effect and safety of electroacupuncture (EA) in the treatment of classical trigeminal neuralgia (CTN).
2. To evaluate whether EA has the advantage over carbamazepine in the immediate effect, long-term effect and post effect of the analgesia in CTN.
3. To demonstrate whether EA has a synergistic effect with carbamazepine on the treatment of CTN, or even whether EA has an alternative effect on carbamazepine.
4. To establish a standardized, effective and convenient therapy program of EA to promote it widely.

Part2. Study program

1. Study subjects

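### The safety inference rests on a chi-square test with no risk difference, confidence interval or upper limit, so a non-significant result could not answer the safety part of objective 1

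*Combined protocol and SAP*

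**What the plan says.** Objective 1 in Part 1 pairs safety with efficacy: "To observe the therapeutic effect and safety of electroacupuncture (EA". It states no safety hypothesis and no tolerable excess.

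The safety output is set in three places in the SAP:

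- **2.2(6)** begins with description: a "list describes four groups of adverse events and adverse reactions", including case numbers and laboratory values that move from normal to abnormal. It then adds statistical "analysis of the adverse reactions by chi-square test".
- **2.2(1)** compares the four groups on total loss and on loss due to adverse events.
- **2.3(2)** gives the methods for count data: "Using the chi-square test, Fisher exact test and so on". 2.3(4) gives the rule for reading them: "All the statistical tests were double-sided, and the p-value is less than or equal to 0.05".

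No section plans a risk difference, a confidence interval or an upper limit for adverse reactions. None gives an expected reaction rate, and none says whether the test compares four groups, single arms, or EA with sham EA pooled across the drug factor. Protocol 2.1 derives the sample size from VAS means and a standard deviation, and ends with "the sample size was enlarged by 20% to 30 cases in one group, in total 120 cases for 4 groups".

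**The concern.** For efficacy, a significant difference is the favourable result and a type I error rate guards it. For safety, the favourable result for EA is the absence of a difference, and nothing in the plan limits how often a real excess would go undetected. A p-value sorts the result into significant or not. It does not say how large an excess is still compatible with the data.

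The stakes come from the other objectives. Objective 3 asks whether EA adds to carbamazepine or can replace it, and objective 4 looks to wide use. Both depend on a statement about harm. If that statement is a test result alone, the report cannot say what excess of adverse reactions has been excluded.

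**Working it through.** **Inputs from the documents.** There are 30 patients per arm and four arms allocated 1:1:1:1 (protocol 2.1). The design is a 2x2 factorial, so EA v sham EA can be pooled as 60 v 60. The test is chi-square (SAP 2.2(6)), or Fisher's exact test for counts (2.3(2)), two-sided at 0.05 (2.3(4)).

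**The plan's own figure.** There is no safety power or safety sample size to reproduce. The only planned figure used here is 30 per arm, and its dropout step is consistent: 24/(1 - 0.20) = 30. Whether 24 is right for efficacy is a separate question and does not affect this point.

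**Assumed.** The documents give no adverse-reaction rates, so a range is shown.

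**Step 1: chance of p > 0.05.** For true rates p1 and p2 and n per side, sum Bin(i; n, p1) x Bin(j; n, p2) over all pairs of counts (i, j) that give p > 0.05. Pearson chi-square without continuity correction uses z = (i - j)/n / sqrt(2 pbar(1 - pbar)/n), with pbar = (i + j)/(2n).

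| Comparator v EA rate | Excess | 60 v 60, chi-square | 30 v 30, chi-square |
|---|---|---|---|
| 3% v 9% | tripling, 6 points | 73% | 87% |
| 5% v 15% | tripling, 10 points | 54% | 74% |
| 10% v 20% | doubling, 10 points | 67% | 81% |
| 20% v 30% | 1.5 times, 10 points | 75% | 86% |
| 10% v 30% | tripling, 20 points | 20% | 50% |
| 15% v 45% | tripling, 30 points | 4% | 26% |

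Fisher's exact test misses more. At 60 v 60 it gives 67% for 5% v 15%, 75% for 10% v 20%, and 27% for 10% v 30%.

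**Step 2: when a tripling is missed more often than not.** At 30 v 30 this needs a comparator rate below about 10% (about 12% with Fisher). At 60 v 60 it needs a rate below about 5-7%, the upper end applying to Fisher. A 10-point excess is missed more often than not at each base rate shown (5%, 10% and 20%), in both comparisons.

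**Step 3: what an interval adds.** Take 9/60 v 3/60 (15% v 5%).

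- Test: pbar = 12/120 = 0.10; standard error = sqrt(2 x 0.10 x 0.90/60) = 0.0548; z = 0.10/0.0548 = 1.83; p = 0.068. Fisher gives p = 0.125.
- Wilson 95% limits: 8.1% to 26.1% for 9/60, and 1.7% to 13.7% for 3/60.
- Newcombe lower limit: 0.10 - sqrt((0.150 - 0.081)^2 + (0.137 - 0.050)^2) = -0.011.
- Newcombe upper limit: 0.10 + sqrt((0.261 - 0.150)^2 + (0.050 - 0.017)^2) = 0.216.

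The test says not significant. The interval says that an excess of up to 21.6 percentage points has not been excluded.

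**Step 4: zero events.** The exact two-sided 95% upper limit is 1 - 0.025^(1/n). It is 6.0% for 0/60 and 11.6% for 0/30.

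**The case against.** The other side has four fair arguments.

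1. **The test is not the whole safety output.** The plan also lists events and reactions by group and compares losses due to adverse events. That is right. With counts per arm, a reader could compute an interval. But listed counts carry no statement of uncertainty, and the comparison of losses covers only events that led to withdrawal. Neither fills the gap.

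2. **No written rule equates p > 0.05 with safety.** A reader might infer that the plan would declare EA safe on a non-significant test. The documents do not support this: objective 1 speaks of observing safety, and SAP 2.3(4) says only when a difference counts as significant. What stands is narrower. The plan supplies no other way of interpreting a null result and no guard against that reading.

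3. **The test is not blind to every large harm.** A reader might infer that a tripling would usually be missed at this sample size. That depends on a comparator rate the documents do not give. The recorded reactions include common complaints such as dizziness, nausea and drowsiness, so a rate above 10% for any reaction is possible, and there a tripling would be found more often than not. Nor does the pooled comparison always miss far more than 20%: for 10% v 30% it misses 19.8%.

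4. **Low power for harm is ordinary in a 120-patient efficacy trial, and an interval does not raise it.** This is also true. The case for the interval is that it shows what has and has not been excluded. A test result alone does not.

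**Conclusion.** The point holds as a gap in how safety will be estimated and reported. The plan has a significance test for adverse reactions but no effect estimate with an interval, on a trial not sized for harm. A non-significant result would therefore leave the safety part of objective 1 unanswered.

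Its size depends on assumed rates. It is serious for less common reactions and for moderate excesses, and small for a tripling of a reaction already seen in 15% or more of comparator patients. The calculations assume full recruitment of 30 per arm, independent patients, and an uncorrected Pearson test unless Fisher is stated. The change is cheap and worth making; it does not touch the efficacy analysis.

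**What to change.** Amend SAP 2.2(6) as follows:

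- Report the risk difference with a two-sided 95% Newcombe or exact confidence interval for EA v sham EA and for carbamazepine v placebo, both pooled over the other factor and by arm. Do this for any adverse reaction and for each listed reaction.
- For reactions with zero events, give the exact upper 95% limit per arm.
- Keep the chi-square or Fisher p-value as descriptive.
- State that a non-significant test will not be reported as evidence of safety, and that the conclusion will give the largest excess risk not excluded by the interval.

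The cost is SAP wording and a few lines of SAS on data already collected, with no extra patients or visits. The downside is that the limits will be wide at 30 or 60 per side, so the safety statement becomes less favourable than a bare non-significant p-value would suggest.
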